8 INTERVENTION DISCONTINUATION

The study will be halted if three grade 3 AEs are identified and determined to be probably related or definitely related to the study interventions (distinct from surgical complications). The PI will notify NIA and the IRB immediately when the third grade 3 event is reported, and enrollment screens will stop accepting new study participants.

Participants may voluntarily withdraw/stop participation at any time and for any reason (noted on consent form). If participants withdraw, we will make every effort to obtain permission and convince them to complete planned evaluations and will try counseling patients to re-enroll in the study if possible. We will also make every effort to continue monitoring and treating AE/SAE for participants who withdraw.

There will be no replacement of participants who withdraw early. Additionally, we will continue to follow participants, with their permission, even if the study intervention is discontinued.

List criteria for discontinuing the study intervention/product (e.g., development of toxicities, study closure by institute) for a participant and methods for determining when criteria are met.

If relevant, include criteria for temporary discontinuation of treatment and define its length.

Also note that subjects may withdraw voluntarily from participation in the study at any time and for any reason. Participants should continue to be followed, with their permission, even if the study intervention is discontinued. Discuss any modifications to the schedule and duration of continued follow-up and indicate the evaluations to be completed while the participant is either temporarily or permanently discontinued from study intervention but followed for outcomes, if applicable.

This section should also include a discussion of replacement of subjects who discontinue early, if replacement is allowed.

Note: It is vital to collect safety data on any subject discontinued due to an AE or SAE. In any case, every effort must be made to undertake protocol-specified safety follow-up procedures. If voluntary withdrawal occurs, the subject should be asked to continue scheduled evaluations, complete an end-of-study evaluation, and be given appropriate care under medical supervision until the symptoms of any AE resolve or the subject's condition becomes stable.

9 STATISTICAL CONSIDERATIONS

9.1 General Design Issues

9.1.1 General approach

This is a two-arm (parallel) pilot randomized trial where adults aged 65 years and older are assigned to have their inguinal hernias repaired under either local (arm 1) or general anesthesia (arm 2).

9.1.2 Central hypothesis

The overarching hypothesis driving design of this study is that performing inguinal hernia surgery under local rather than general anesthesia for patients aged 65 years and older will

significantly reduce operative and recovery time, will lead to fewer complications, and will lead to better cognitive and physical recovery from surgery. This hypothesis will eventually be tested in a multisite randomized trial whose design will be informed by this pilot randomized trial.

The hypothesis for this pilot study is that we will be able to successfully recruit, randomize, and retain enough patients for a fully powered multisite randomized trial. Additionally, we plan to test study procedures for screening, enrollment, randomization, outcome measurement, and retention while also evaluating whether we can reduce the study burden by eliminating some of the study instruments. We also hypothesize that, although the pilot study (by definition) is not powered to detect differences between groups, that the local anesthesia group will have fewer complications and better physical and cognitive function (though the difference may not be statistically significant).

9.1.3 Justification for pilot design

The chances of completing a successful multisite randomized clinical trial are increased by testing study procedures and processes on a smaller scale prior to conducting a fully powered trial.^{18,19} This will enable us to identify and address problems prior to initiating the fully powered study. Conducting a pilot study also allows us to test study instruments and potentially reduce the time burden at each evaluation visit by determining whether study measures are statistically redundant (the other measures explain a substantial portion of one measure's variance). Reducing the time burden for participants is an important step to enhance the completeness of data collection by minimizing missing data and reducing withdrawals from the study.

As outlined below and in the attached grant proposal, data from the pilot study will also be used for preliminary estimation of effect sizes for the future randomized trial. As the pilot is, by definition, not fully powered to detect all relevant differences between groups, this analysis is entirely exploratory.

9.1.4 Primary outcomes and hypotheses

- 1) Outcome: Rates of enrollment
 - a. Hypothesis: Based on our preliminary data, at least 75% of eligible patients will agree to be randomized.
- 2) Outcome: Proportion of participants completing all study visits
 - a. Hypothesis: We will be able to follow 100% of patients up to their 2 week postoperative visit (as essentially all patients keep this appointment in our clinical practice), and we will be able to follow at least 90% of patients at the six month time point.
- 3) Outcome: Proportion of missing data
 - a. Hypothesis: Missing data on study instruments will be <5%
- 4) Outcome: Time to complete study evaluations and instruments
 - a. Hypothesis: Total time to complete each study evaluation will be acceptable to patients and <30 minutes.
- 5) Outcome: Participant satisfaction with study procedures and instruments
 - a. Hypothesis: Overall time burden for instrument completion will be acceptable to patients

- 6) Outcome: Whether survey instruments can be eliminated due to redundancy
 - b. Hypothesis: One or more study instruments can be eliminated (thus reducing the time burden) because the other instruments may predict a substantial portion of variance
- (7) Outcome: Estimate sample size for fully powered randomized trial.
 - a. Hypothesis 1: Using data from the pilot study, we will be able to establish stable estimates of the necessary sample size for a randomized trial.
 - b. Hypothesis 2: We will be able to identify the optimal primary outcome for a multisite randomized trial by balancing the necessary sample size needed to adequately power the study versus the clinical significance of each outcome.

9.1.5 Secondary outcomes and hypotheses

Again note that this pilot trial is not powered to detect differences in the secondary (clinical) outcomes described below. Our hypotheses reflect expected findings for a larger, multisite randomized clinical trial that will follow this pilot study.

- 1) Outcome: Quality of life
 - a. Hypothesis: quality of life will be significantly improved when older adults have their inguinal hernias repaired under local rather than general anesthesia.
- 2) Outcome: Physical function
- 3) Hypothesis: physical function (activities of daily living) will be significantly improved when older adults have their inguinal hernias repaired under local rather than general anesthesia.
- 4) Outcome: Cognitive function
 - a. Hypothesis: Cognitive function will be significantly improved when older adults have their inguinal hernias repaired under local rather than general anesthesia.
- 5) Outcome: Pain
 - a. Hypothesis: Pain will be similar for older adults having hernia surgery regardless of anesthesia modality.
- 6) Outcome: Postoperative complications
 - a. Hypothesis: The overall incidence of postoperative complications will be significantly reduced when older adults have their inguinal hernias repaired under local rather than general anesthesia. This will mostly be due to decreased rates of urinary retention (a common complication of general anesthesia).
- 7) Outcome: Operative and anesthesia times
 - a. Hypothesis: Time for surgery (incision to closure) and anesthesia (enter to exit operating room) will be significantly decreased when older adults have their inguinal hernias repaired under local rather than general anesthesia.
- 8) Outcome: Recovery time (time spent in the post-anesthesia care and stepdown units)
 - a. Hypothesis: Time spent in the post-anesthesia care and stepdown units after surgery will be significantly decreased when older adults have their inguinal hernias repaired under local rather than general anesthesia.

State the statistical hypotheses.

Describe the reasons for choice of study design (e.g., parallel groups, crossover, immediate versus deferred intervention, factorial, large simple trial, equivalency or non-inferiority trial); why certain design features were chosen (e.g., for a crossover trial, how the length of the washout period was chosen).

Describe the primary and secondary hypotheses and the primary and secondary outcome measures as well as their validity and reliability.

9.2 Sample Size and Randomization

Describe sample size calculation and effect size with respect to power. Specify the test statistic; Type I and Type II error rates; assumed event rate event rate for dichotomous outcome (mean and / or variance for continuous outcome) for each study arm; assumed rates of drop-out, withdrawal, cross-over to other study arms, missing data, etc.; and approach to handling withdrawals and protocol violations, in terms of an “intent to treat” approach.

9.2.1 Treatment Assignment Procedures

We will randomly assign older patients having inguinal hernia surgery to one of the two study arms: (1) local anesthesia or (2) general anesthesia. Our goal for enrollment will be a total of 80 participants with 40 participants in each arm and a total of 40 participants from each site. We will use a stratified randomization scheme with blocking within strata. Stratification factors include hospital location (Dallas or Houston) and age (65-75 or 75+ years). Equal allocation by strata will be used so that differences among hospitals and age groups will be balanced. Randomized assignments will be generated ahead of time for each combination of strata and placed within stored and numbered envelopes kept at each hospital location. We will generate 20% more assignments than necessary to allow for potential withdrawals. Before patients are enrolled, physicians, patients, and research coordinators will not know which anesthesia modality will be assigned. Once patients are enrolled, the next envelope that applies to that participant (based on stratification factors) will be selected and labeled with the date and time of enrollment, the patient’s name, and the research team member responsible for enrollment. The labeled and unopened envelope will be photographed for our records and the envelope number will be recorded in the participant’s record.

9.2.1 Masking treatment assignment

Although the patient and operating team (surgeon, anesthesiologists, nurses) will unavoidably be aware of which study arm participants are assigned to, the investigative team will remain blinded to treatment assignment at all times. Research assistants collecting baseline, peri-, and postoperative outcomes will be blinded to study assignment when conducting their assessments. For the baseline assessment, the research assistant will not open the envelope containing the treatment assignment until the baseline assessment is complete. For subsequent assessments, a different research assistant will interact with the patient. The investigator and study team will also be blinded to treatment assignment until after data analysis is complete, with the exception of the statistician ([name]) who will be analyzing the data. All study results will be presented to the investigator and DSMB with patients identified as belonging to “group A” or “group B”

and the assignment will remain masked until the final analysis is complete and the findings are ready for publication.

9.2.2 Sample

There is no widely accepted method for estimating statistical power for a pilot study since, by definition, it is not powered to detect significant differences between groups. Instead, the goal is to demonstrate feasibility of conducting a fully powered trial and to provide some baseline information that can assist with estimation of the final sample size for the multisite trial. However, our sample size of 80 patients over 2 years (20 patients per site per year) does provide 80% power at $\alpha < 0.05$ for a 30 minute difference in operative and recovery time, assuming a common standard deviation of 45 minutes and a total operating + post-anesthesia unit time of 180 minutes for the general anesthesia group (consistent with our preliminary data). We would also have 80% power to detect a 5-point difference in quality of life on the Carolinas Comfort Scale, given prior published data on this instrument.^{20,21} Additionally, we generated 1000 bootstrap samples using data from our prior retrospective study comparing local versus general anesthesia for hernia repair. Each sample contained 40 patients who had surgery under local anesthesia and 40 under general anesthesia. We then evaluated the range of estimated mean and standard deviation for total operative and recovery time across all 1000 samples and found that the mean range (156-205 minutes) and standard deviation (42-113) provided reasonable and stable estimates for the actual values in the original sample. This provides further evidence that a sample size of 80 patients would provide reasonable data for estimating sample size for a fully powered multisite randomized trial.

Describe the treatment assignment procedures (randomization, minimization, relevant criteria, etc). If such procedures are proposed describe rationale as well as the procedure.

Plans for the maintenance of trial randomization codes and maintaining appropriate masking for the study should be discussed, including the timing and procedures for planned and unplanned breaking of randomization codes should be included. Include a statement regarding when unmasking may occur and who may unmask.

If the randomization will be stratified, indicate whether (and why) there is a sample size goal for each stratum. Identify what factors (if any) will be used to stratify the randomization.

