6.2.3 Follow-up Visits

- Visit 2 (During Surgery)
 - The second set of assessments will occur during the normal course of clinical care for inguinal hernias (this does not represent an additional study visit on top of the usual care). During the surgery, the

anesthesiologist automatically records data on the below information as part of the routine anesthesia record.

- Vital signs: maximum, minimum, and median values for systolic and diastolic blood pressure and heart rate
 - Total operating room time: the difference between the time the patient enters the operating room and the time the patient leaves the operating room
 - Time for surgery: the time from the start of the operation (skin incision) and the end of the operation (skin closure)
 - Adverse events, serious adverse events, and intraoperative complications
 - Volume of fluids administered
 - Minimum alveolar concentration of volatile anesthetic
 - Dose of local anesthesia used
- Visit 3 (After Surgery & Before Same Day Discharge)
 - Inguinal hernia repair is typically an outpatient procedure where the patient is observed for several hours to ensure that there are no immediate complications of surgery or anesthesia and that patients are able to ambulate, tolerate oral intake, and manage basic self-care with assistance from family or other caregivers. From the time the patient leaves the operating room until the time the patient leaves the hospital, we will assess the following:
 - Vital signs: We will record any episodes of hypotension (mean arterial pressure <60) or hypertension (systolic blood pressure >180 or diastolic > 110), fever (temperature >101.6 F), tachycardia (heart rate >120), or poor oxygenation (oxygen saturation on pulse oximetry <85%). This information will be obtained from the post-anesthesia care unit and stepdown unit records.
 - Delirium and cognitive assessment: we will administer a battery of tests to assess (1) cognitive function (overall and particular domains including processing, visual scanning, attention, mental set-shifting, executive function, and verbal memory) and (2) delirium risk
 - Confusion Assessment Method (short form)
 - Montreal Cognitive Assessment (5-minute version)
 - Trail Making Tests Parts A and B

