 - Time in post-anesthesia care unit: after surgery, all patients who had their operations performed under general anesthesia are observed in a unit with a nurse:patient ratio of $\leq 2:1$, similar to intensive care units. This level of nursing care is required to quickly detect immediate complications of anesthesia, including respiratory failure and hypotension. Our research assistants will use the nursing records to determine what time the patient entered the unit and what time they were transferred to the next phase in care: the step-down unit. Patients having

surgery under local anesthesia are sent directly from the operating room to the step-down unit.

- Time in step-down unit: Once general anesthesia patients meet criteria in the post-anesthesia care unit (awake, normal respiratory drive and blood pressure), they are transferred to the step-down unit. All local anesthesia patients are transferred directly to the step-down unit once their operation is complete. In this unit, patients are provided food and liquids to test their ability to tolerate oral intake. Patients also are asked to ambulate and void to ensure that they are capable of self-care and have not developed urinary retention. Our research assistants will use nursing records to identify the time of entry and departure from the step-down unit.
 - Urinary function/unplanned catheterization: research assistants will review nursing notes to determine whether patients were able to void or whether they required assistance. Our standard clinical protocol is that if patients have not urinated by 4 hours after surgery, they will undergo a bladder scan. If >200cc of urine is found in the bladder, the patients undergo in-and-out catheterization and are observed until they void again. If still unable to void, the patient has a foley catheter placed, is started on medication for prostatic hypertrophy, and arrangements are made with the urology service to undergo outpatient voiding studies and removal of the catheter within 1-2 weeks.
 - Unplanned admission: since most inguinal hernia surgeries are outpatient procedures, our nursing assistants will check the medical record the day after surgery to see if the patient was able to leave or was admitted. If admitted, we will contact the team to determine the reason for admission.
 - Adverse events and serious adverse events
- Visit 4 (48 Hours After Surgery)

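### Section 9.2.2 calls bootstrap SDs of 42 to 113 minutes stable, but they imply widely different trial sizes, and the SD of 45 used for power lies near the bottom of that range

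*Combined protocol and SAP*

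**What the plan says.** Section 9.2.2 states that the pilot is not powered for differences between groups, then offers two kinds of quantitative support for 80 patients.

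- **Power.** It claims 80% power "for a 30 minute difference in operative and recovery time, assuming a common standard deviation of 45 minutes", together with "a total operating + post-anesthesia unit time of 180 minutes for the general anesthesia group (consistent with our preliminary data").
- **Bootstrap.** It drew 1000 samples of 40 local and 40 general anesthesia patients, "using data from our prior retrospective study comparing local versus general anesthesia for hernia repair". It reports: "We then evaluated the range of estimated mean and standard deviation for total operative and recovery time across all 1000 samples". The conclusion is that "the mean range (156-205 minutes) and standard deviation (42-113) provided reasonable and stable estimates for the actual values in the original sample", and hence that "a sample size of 80 patients would provide reasonable data for estimating sample size" for the multisite trial.

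The section does not print the SD of the retrospective sample. It does not say whether the ranges are for the pooled 80 or for arms of 40, and it sets no criterion for stability.

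Estimating the multisite sample size is primary outcome 7, and section 9.1.4 hypothesises that the estimates will be stable. For that outcome, section 9.4.1 plans means and SDs for continuous variables, and confidence intervals only for proportions.

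**The concern.** Two things look wrong. First, an SD that varies from 42 to 113 between resamples is a poor basis for calling the resulting sample size stable. Section 9.2.2 is the plan's only quantitative argument that 80 patients can deliver primary outcome 7.

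Second, the power statement uses an SD only 3 minutes above the smallest of 1000 bootstrap SDs. The time variable also carries two labels. The 30-minute difference and the bootstrap refer to operative and recovery time, while the 180-minute mean refers to operating plus post-anesthesia unit time. Sections 1.2 and 9.4.2 count step-down time as part of recovery. Section 6.2.3 says "All local anesthesia patients are transferred directly to the step-down unit once their operation is complete", so including or excluding step-down changes what is compared between the arms.

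At stake is an assurance of precision that would pass to the planning of the main trial without any statement of its uncertainty.

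**Working it through.** **Inputs from section 9.2.2:** difference 30 minutes, SD 45, 40 per arm, alpha 0.05, bootstrap means 156–205 and SDs 42–113. Two-sided testing is assumed because the plan does not state it. Results are for the two-sample t-test (noncentral t) unless noted.

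**1. The plan's own figure.** At SD 45, power is 83.8% with 40 per arm and 79.7% with 36 per arm. Section 9.2.2 states no dropout; 36 would correspond to an assumed 10% loss. The 80% is therefore correct as *at least 80%*. Solving for the SD at which 40 per arm gives exactly 80% yields 47.3 (47.9 by the normal approximation).

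**2. Sample size at the printed extremes.** Approximately, n per arm = 2 × (1.960 + 0.842)² × (SD/30)²; the t-test adds about one patient.

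| SD | normal approximation | t-test, rounded up |
|---|---|---|
| 42 | 30.8 | 32 |
| 45 | 35.3 | 37 |
| 113 | 222.7 | 224 |

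The ratio of the extremes is (113/42)² = 7.2.

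**3. Allowing for extremes.** The expected range of 1000 standard normal values is 6.48 standard deviations. Two readings of the printed figures were tried.

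- *Everything from pooled samples of 80.* On the log scale the spread is ln(113/42)/6.48 = 0.153 around √(42 × 113) = 68.9. The central 95% of SDs is 68.9 × exp(±1.96 × 0.153), about 51 to 93. The ratio in n is (93/51)², about 3.3.
- *Means pooled over 80, SDs listed across both arms of 40.* Assumed normal data with SDs of 65 (local) and 82 (general), a 30-minute difference and 150 source patients per arm give bootstrap means of about 153–206 and SDs of 42 to about 110, close to the printed figures. The central 95% range in n from the within-arm SD is then 1.9-fold. Normal data from 80 patients give the same 1.9 by chi-square limits.

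**4. The SD that the ranges imply.** The printed means span 205 − 156 = 49 minutes.

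- Means of 80: 49/6.48 × √80 = 67.6.
- The second reading above: √((65² + 82²)/2) = 74.0.
- Means of 40: 49/6.48 × √40 = 47.8. Normal data with SD 48 in samples of 40 would, however, give SDs of only about 0.65 × 48 = 31 to 1.38 × 48 = 66 over 1000 samples, not 42–113.

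Among simulated sources (several assumed shapes, with and without outlying patients) that reproduced both printed ranges, the lowest SD was 51.9.

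**5. Power at those SDs, 40 per arm, 30 minutes.** SD 51.9: 72%. SD 65: 53%. SD 68: 50%. SD 74: 43%. SD 80: 38%.

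**6. Which time variable.** The bootstrap means centre on (156 + 205)/2 = 180.5, close to the 180 minutes in the power statement. A total that included step-down should be longer, since section 6.2.3 describes an outpatient procedure "where the patient is observed for several hours". This makes a single variable likelier but does not establish it. Whether the retrospective patients resemble those eligible for this trial is not stated.

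**The case against.** The strongest reply is that 42–113 may be no more than ordinary sampling error. On the second reading in step 3 it is: arm-level SDs from plain normal data reproduce the printed range, and the spread in sample size is what any 80 patients would give. This stands, and it rules out treating the 3.3-fold figure as established. It does not rescue SD 45, because the same reading needs SDs of 65 and 82. Nor does a 1.9-fold range in sample size justify calling the estimate stable without qualification.

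A reader might take 32 to 224 per arm as the pilot's real uncertainty. The documents do not support that. The range is described as running across all 1000 samples, so these are apparently a minimum and a maximum.

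A reader might also infer that the 80% is a miscalculation or that SD 45 is wrong. The 80% reproduces. No central SD is printed, and SD 45 may be right for a different time variable or a more selected population. In that case the bootstrap does not support the variable that was powered.

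The power values in step 5 are for a t-test, whereas section 9.5.2 plans the Wilcoxon test. If a few very long times inflate the SD, the rank test may lose less power than these values suggest. How much depends on data the plan does not show.

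Finally, the plan limits its own claims: section 9.1.3 calls the effect-size work exploratory, and section 9.4.1 sizes the main trial from pilot data rather than from SD 45. That limits the consequence. It does not cover primary outcome 7, which is the pilot's own aim and the purpose for which the bootstrap is cited.

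**Conclusion.** The point holds in a limited form. The printed SD range does not support an unqualified claim of stability. The extremes are 7.2-fold apart in sample size, and the central 95% is about 1.9-fold to 3.3-fold, depending on a tabulation that the plan leaves unstated. The fold ratios do not depend on the 30-minute difference; 32 and 224 per arm assume that difference, 80% power and a two-sided 5% t-test.

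The 80% power is correct at SD 45 and lost above about SD 47. Readings that roughly reproduce both printed ranges imply a larger SD, commonly 65 to 80, with t-test power of about 53% to 38%. These implied SDs are reconstructions from two ranges, not documented values. Either the 80% is not supported by the team's own data, or the bootstrap describes another time variable or population and is not evidence for the powered comparison. Section 9.2.2 needs correcting in both cases.

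It would go too far to conclude that the pilot is too small. The pilot's 80 patients and its design are unaffected. What changes is how much precision it can promise for the main trial's sample size.

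**What to change.** In section 9.2.2:

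1. Use one named time variable, stated as with or without step-down, for the 30-minute difference, the SD, the 180-minute mean and the bootstrap.
2. Say whether the bootstrap ranges are pooled or per arm, and whether the retrospective patients meet this trial's eligibility criteria.
3. Report the retrospective SD by arm, with bootstrap 2.5th and 97.5th percentiles in place of 42–113.
4. Restate the power over that SD range.
5. Replace the claim of reasonable and stable estimates with the range of sample sizes that these SDs imply.

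In section 9.4.1, outcome 7, report a 95% confidence interval for the SD of each continuous outcome and the sample-size range it implies. Note that such intervals can cover too little for skewed times. In simulations with 80 patients, nominal 95% normal-theory limits covered 0.85 (lognormal) and 0.51 (normal with outliers); BCa bootstrap limits covered 0.90 and 0.68.

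The cost is a short reanalysis of data the team already holds, some rewording, and probably a less favourable stated power. No extra patients are needed.
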